17.2. LABORATORY EVALUATIONS

17.2.1. POTENTIAL HY'S LAW EVENTS

In addition to the laboratory analyses described in the Master COV-01 SAP for the identification of the potential Hy' law events, the following summary will also be provided:

- Number and percentages of patients with (ALT > 3 x ULN or AST > 3 x ULN) AND (total bilirubin > 2 x ULN) AND (alkaline phosphatase [ALP] < 2 x ULN) at any time after the first dose of study drug and by visit for each treatment arm as well as for the subset of patients randomized to the placebo to zilucoplan + SoC treatment arm.

17.3. VITAL SIGNS

Analysis of vital signs is described in the Master COV-01 SAP.

17.4. ELECTROCARDIOGRAM EVALUATIONS

Analysis of electrocardiogram (ECG) evaluations is described in the Master COV-01 SAP.

17.5. PHYSICAL EXAMINATION

Analysis of physical examination is described in the Master COV-01 SAP.

18. PHARMACOKINETIC ASSESSMENTS

Concentrations of zilucoplan will be summarized descriptively at each scheduled assessment based on the PK analysis set (refer to Section 5.1). Geometric mean (geoMean), geometric coefficient of variation (geoCV) and 95% CI for the geoMean will also be presented in the summaries of zilucoplan concentration data. Geometric coefficient of variation will be reported as a percentage to 1 decimal place and the 95% CI for the geoMean will use the same number of decimal places as the geoMean. It will be left blank if the geoCV is 0.

When reporting individual zilucoplan concentration data in listings and presenting summary statistics in tables, the following rules will apply:

CCI		Version Number:	Amendment 2, v1.0
PPD		Version Date:	28-Jul-2021

CCI [Redacted]

- Missing data should be reported as ‘NV’ (no value) in the listings;
- Concentrations below the lower limit of quantification (LLOQ) should be reported as BLQ (below the limit of quantification) in the listings;
- To calculate summary statistics, BLQ values should be set to half the LLOQ value and missing values should be excluded;
- When the total number of BLQ and missing values exceeds one third of the total then only minimum and maximum should be reported for this scheduled assessment. Other summary statistics should be reported as missing (“-“). The minimum should be reported as BLQ;
- When the mean value includes one or more replaced BLQ values then a footnote should be included to say “contains one or more BLQ values replaced by half the LLOQ value”;
- A minimum of 3 values are required to calculate summary statistics. If only 2 values are available, then these should be presented as the minimum and maximum with other summary statistics reported as missing (“- “).

Zilucoplan concentrations will be listed.

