## 9.0 STATISTICAL CONSIDERATIONS

### 9.1 Sample Size Determination

A total of 350 patients are planned to be randomized to each candidate agent plus SoC. Simultaneously, patients will be randomized to placebo plus SoC throughout the course of the study. The subset of the placebo plus SoC group, regardless of which sub-protocol the placebo belongs, enrolled concurrently to any active agent with matching inclusion/exclusion criteria will serve as its comparator group. The primary efficacy endpoint to compare selected treatments plus SoC to placebo plus SoC will be the time to clinical recovery up to Day 29, ie, fit-for-discharge, as defined by achieving a score of 6, 7, or 8 on the 8-point ordinal scale of clinical severity status, without rehospitalization.

Assuming a median time to clinical recovery of 11 days for patients randomized to an active treatment group plus SoC compared with 15 days for those randomized to placebo plus SoC, 350 patients are needed per arm in order to observe 490 clinical recovery events between the 2 treatment groups being compared at the primary analysis. This sample size will provide approximately 88% power to detect a hazard ratio (HR) of 1.364 for the occurrence of the clinical recovery events, when comparing each candidate agent plus SoC with placebo plus SoC, at a 1-sided significance level of 0.025.

This sample size will provide the following information about the key secondary endpoints: assuming the oxygen-free recovery rate at Day 29 is 65% for the placebo plus SoC group, a sample size of 350 patients per arm will provide approximately 80% power to detect a 9.7% absolute increase in the proportion of patients who have oxygen-free recovery at Day 29 among the active treatment group plus SoC group. Assuming 70% of patients randomized to placebo plus SoC achieve at least 2-point improvement from baseline on the 8-pt ordinal scale or being fit-for-discharge at Day 29, 350 patients per arm will provide approximately 80% power to

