Blood (EDTA and SST) for zilucoplan concentration analysis (PK), pharmacodynamic, and exploratory biomarkerst		X	Days 3 and 8 (± 1 day) while hospitalized, and day of discharge	X u	X u	

	Screening	Baseline				
Day (± Window)	Day -1 or Day 1	Day 1	Daily Until Hospital Discharge (or Daily Until Day 29 While in Hospital)	Day 15 a (± 2 days)	Day 29 a (± 3 days)	Day 60 a (± 4 days) (End of Study)
Blood (SST) ADA		X	Day of discharge	X u	X u	
CCI						

ADA = anti-drug antibody; ARDS = acute respiratory distress syndrome; C = component; COVID-19 = coronavirus disease 2019; ECG = electrocardiogram; eCRF = electronic case report form; EDTA = ethylenediaminetetra-acetic acid; FiO2 = fraction of inspired oxygen; G-CSF = granulocyte colony-stimulating factor; GM-CSF = granulocyte-macrophage colony-stimulating factor; ICU = intensive care unit; IFN $\gamma$  = interferon gamma; IL = interleukin; IL-1RA = interleukin-1 receptor antagonist; IP-10 = interferon gamma-induced protein 10; MASP = mannose-associated serine protease; MCP-1 = monocyte chemoattractant protein 1; MIP-1a = macrophage inflammatory protein 1a; **CCI**; PK = pharmacokinetic; SARS-CoV-2 = severe acute respiratory syndrome coronavirus 2; SoC = standard of care; SpO2 = oxygen saturation; SST = serum-separating tubes; TNF $\alpha$  = tumor necrosis factor alpha.

Note: Additional assessments for this sub-protocol are highlighted in bold and italics.

- a These visits will be performed even if a patient has already been discharged. If discharged prior to scheduled visit, these visits will be conducted via telemedicine. For visits conducted by telephone, it may not be possible to perform some scheduled assessments (eg, vital signs). The Day 29 assessments will also be performed, where possible, for patients who discontinue the study prematurely.
- b Medical history includes estimated date and time of first COVID-19 related symptoms and co-morbidities (eg, respiratory [including date of diagnosis of ARDS, if present], cardiovascular, metabolic, malignancy, endocrine, gastrointestinal, immunologic, renal).

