n Hematology, clinical chemistry, liver function tests, cardiac panel, and coagulation.

o Any laboratory tests performed as part of routine clinical care can be used for safety laboratory testing.

p Hematology, clinical chemistry, and liver function tests.

q If not done or entered into the eCRF form within previous day.

r Hematology, clinical chemistry, and liver function tests will be collected on the eCRF, if available, while the patient is in hospital.

s This assessment will be performed on Day 15 or date of discharge, if earlier.

t CCI

*" This assessment will be performed if the patient is in the hospital.*

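### The zilucoplan PK table rule counts missing samples as if they were below quantification, so a visit with no BLQ result can lose most of its statistics and show a false minimum of BLQ

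*SAP*

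**What the plan says.** Section 18 of the COV-01-005 SAP gives the rules for summarizing zilucoplan concentrations at each scheduled assessment in the PK analysis set:

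- For calculation: "BLQ values should be set to half the LLOQ value and missing values should be excluded".
- For suppression: "When the total number of BLQ and missing values exceeds one third of the total then only minimum and maximum should be reported". Beyond that point, "Other summary statistics should be reported as missing" and "The minimum should be reported as BLQ".
- For sparse visits: "A minimum of 3 values are required to calculate summary statistics". With only two values, those two are shown as minimum and maximum.
- For listings: a missing value is shown as NV and a result under the LLOQ as BLQ.

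The SAP defines neither the total nor a missing value for the suppression rule.

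The sub-protocol's Schedule of Activities (section 1.2) takes PK blood on Day 1 and then "Days 3 and 8 (± 1 day) while hospitalized, and day of discharge". For Days 15 and 29 the footnote reads: "This assessment will be performed if the patient is in the hospital". The PK analysis set (COV-01-005 SAP 5.1) needs only one post-baseline concentration, so patients discharged early stay in it.

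**The concern.** A suppression rule for BLQ values exists because a mean built on many substituted values says little. A missing sample involves no substitution and tells us nothing about whether concentrations were low. Adding it to the BLQ count removes statistics for a reason unrelated to the assay. Labelling the minimum BLQ then states something about exposure that no measurement supports.

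At stake is the descriptive account of exposure to the fixed 32.4 mg daily dose, which runs to Day 14 or discharge. A reader of the tables would see BLQ as the lowest value in dosed patients at a visit where every sample may have been quantifiable.

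**Working it through.** **The text.** Take a visit with no BLQ result and more than one third of values missing.

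- Calculation bullet: drop the missing values and summarize the rest.
- Suppression bullet: count the missing values, print only minimum and maximum, and set the minimum to BLQ.
- Listing rule: NV for the missing values, and no BLQ anywhere.

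The table minimum then contradicts the listing. The two-value case shows a second conflict. With two quantifiable results and over a third missing, the sparse-visit bullet prints the lower result as the minimum, while the suppression bullet prints BLQ.

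**How much is missing.** The plan gives no figure to reproduce here. I applied the rule literally with zero BLQ results and asked what share would be missing through discharge alone.

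Inputs:
- Threshold: more than 1/3 (COV-01-005 SAP 18).
- Medians m: 11 days on active, "Assuming a median time to clinical recovery of 11 days for patients randomized to an active treatment group plus SoC", and 15 days on placebo (Master Protocol 9.1). Their ratio, 15/11 = 1.364, equals the stated hazard ratio, as exponential times would give.
- Assumptions: exponential times, discharge at recovery, total = PK analysis set, every post-discharge sample counted as missing.
- Mapping: Master SAP 6.4 uses discharge data for a scheduled visit whose own value is absent. The schedule's windows are ±1 day (Day 8), ±2 (Day 15) and ±3 (Day 29).

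Formula: missing share = 1 − 2^(−t/m). Without mapping, t is the visit day or one day less. With mapping, t is the last day before the window opens: 6, 12 and 25.

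| Visit | m = 11, no mapping | m = 15, no mapping | m = 11, mapped | m = 15, mapped |
|---|---|---|---|---|
| Day 8 | 36-40% | 28-31% | 31% | 24% |
| Day 15 | 59-61% | 48-50% | 53% | 43% |
| Day 29 | 83-84% | 73-74% | 79% | 69% |

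Examples: Day 15, m = 11, t = 15 gives 1 − 2^(−15/11) = 61%. Day 8 mapped, m = 11, t = 6 gives 1 − 2^(−6/11) = 31%. At Day 3 (t = 3) the shares are 17% and 13%. If the windows are widened to the midpoint between visits, Day 8 (t = 5) falls to 27% and 21%, and Day 15 (t = 11) to 50% and 40%.

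The one-third line is crossed at t = m × log2(1.5), which is 6.4 days for m = 11 and 8.8 days for m = 15. So Days 15 and 29 trigger in every column, Day 3 in none, and Day 8 only with the shorter median and no mapping.

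**Illustration.** The documents do not state the size of the PK set, so assume 54 patients (an even split of the 108 randomized). At Day 15 with m = 11 and no mapping, 54 × 2^(−15/11) = 21 are measured and 33 are missing. With none BLQ, 33/54 = 61% and the rule fires. All 21 values are quantifiable, yet the minimum prints as BLQ. Counting BLQ values over reported results gives 0/21 = 0%, and the rule does not fire.

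**The other reading.** If the total is samples due, discharge contributes nothing. The rule then fires only when more than a third of due samples have no result. With 21 due, 8 without a result is enough (8/21 = 38%); 7 is not (7/21 = one third exactly). Such gaps are foreseen: Master Protocol 8.6 does not treat refusal or logistical failure of PK sampling as a violation, and sub-protocol 4.2 allows analysis of only a selected set of samples.

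**The case against.** The strongest reply is that a sample never due after discharge need not be a missing value for that assessment. If so, the discharge mechanism disappears. That stands as a possible reading, and it is why the size is conditional. It does not rescue the rule: the total cannot mean only results in hand, since missing values are counted against it, and the unconditional BLQ label fails under any reading.

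The proxy is also weak. Recovery includes score 6, where the patient is still in hospital and can be sampled, so equating recovery with discharge overstates missingness. The medians are design assumptions, not observations. This stands.

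A third reply is that late samples come only from patients still in hospital, so withholding means there is defensible. That could justify a rule on missingness, stated as such, but not calling the minimum BLQ.

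Three stronger readings are tempting, and the documents do not support them:

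- That every statistic is lost. The maximum is kept, and the listings still separate NV from BLQ.
- That Day 8 is lost. Once discharge samples are mapped, the estimate is below one third under both medians.
- That about 94 zilucoplan patients are affected, from splitting 108 at 7:1 (108 × 7/8 = 94.5). The 7:1 in COV-01-005 SAP 4.5.2 compares the active arm with the shared control arm under the Master SAP definition. It is not the split of the 108, and the PK set has its own entry condition.

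**Conclusion.** The rule is wrong as written. It can suppress valid statistics and print a false minimum at a visit with no BLQ result, and it conflicts with the bullet before it. This rests on the text alone.

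The expected reach rests on assumptions. With the PK set as the total, and exponential recovery standing in for discharge, Days 15 and 29 are likely to trigger and Day 8 may not. With samples due as the total, the fault needs refusals, losses or unanalysed samples.

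The consequence is modest. A reader might infer that exposure data are discarded or that efficacy conclusions suffer. Neither follows: individual concentrations are listed, population PK modelling remains open under sub-protocol 4.2, and the COV-01-005 SAP plans no efficacy inference. Only cells in descriptive PK tables are affected. The point still merits correction, because the error is definite and cheap to remove.

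**What to change.** Amend section 18 of the COV-01-005 SAP:

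1. Apply the one-third rule to BLQ values only, with the number of patients who have a reported result at that assessment as the denominator.
2. Leave missing values out of both counts and show n at each assessment.
3. Print the minimum as BLQ only when at least one result at that assessment is BLQ; otherwise print the observed minimum.
4. Keep the three-value rule, which already protects sparse visits.

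The cost is about two sentences and one programming condition. The downside is that Day 15 and Day 29 statistics will describe only patients still in hospital; a table footnote should say so.

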18.1. DERIVATION

The geoCV, in percentage, will be calculated using the following formula where SD is the standard deviation from the log-transformed data:

- $GeoCV (\%) = \sqrt{\exp(SD^2) - 1} \times 100$

19. PHARMACODYNAMIC AND OTHER BIOMARKER ASSESSMENTS

CCI [Redacted]

[Redacted]

[Redacted]

[Redacted]

[Redacted]

[Redacted]

[Redacted]

CCI [Redacted]

PPD [Redacted]

Version Number: Amendment 2, v1.0
Version Date: 28-Jul-2021

CCI [Redacted]

[Redacted]

[Redacted]

CCI

20. ANTI-DRUG ANTIBODY TESTING

Number and percentage of patients with a negative ADA response (i.e., either [negative screen] or [positive screen and negative immunodepletion]) and a positive ADA response (i.e., positive screen and positive immunodepletion) will be summarized by scheduled visit and treatment arm based on the ADA analysis set (refer to Section 5.3).

Number and percentage of patients in each of the following categories will also be summarized by treatment arm:

1. Treatment-induced ADA negative, defined as patients who were ADA negative at baseline as well as at all post-baseline scheduled visit;
2. Treatment-induced ADA positive, defined as patients who were ADA negative at baseline and ADA positive at at least one post-baseline scheduled visit. This category also includes patients with a missing ADA response status at baseline who had at least one ADA positive response at any post-baseline scheduled visit;
3. Treatment-reduced ADA, defined as patients who were ADA positive at baseline and ADA negative at all post-baseline scheduled visit;
4. Treatment-unaffected ADA, defined as patients who were ADA positive at baseline and ADA positive at at least one post-baseline scheduled visit with titer values of the same magnitude as baseline (i.e., equal or less than a pre-defined fold difference increase from the baseline value, where the pre-defined fold difference increase from the baseline value is defined as the minimum significant ratio [MSR] determined during assay validation);
5. Treatment-boosted ADA positive, defined as patients who were ADA positive at baseline and ADA positive at at least one post-baseline scheduled visit with increased in titer values as compare to baseline (i.e., greater than the pre-defined fold difference increase from baseline value);
6. Inconclusive, defined as patients who were ADA negative or positive at baseline for whom some post-baseline ADA response assessments are missing, while all other post-baseline ADA response assessments are ADA negative;
7. Total prevalence of pre-Ab i.e., patients in categories 3, 4, and 5 combined;
8. Total incidence of treatment-emergent ADA positive i.e., patients in categories 2 and 5 combined.

CCI

PPD

Version Number: Amendment 2, v1.0
Version Date: 28-Jul-2021

CCI

CCI [Redacted]

The fold difference increase from baseline (i.e., the MSR determined during the assay validation) needed to consider a titer value reported post-baseline to be above the assay validation will be noted in the relevant tables and listings.

All ADA data will be listed.

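### Zilucoplan ADA categories: pre-existing antibody prevalence leaves out known baseline positives, and the all-visits rule for categories 1 and 3 does not fit a schedule that stops sampling at discharge

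*SAP*

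**What the plan says.** COV-01-005 SAP, section 20, defines category 1 (ADA negative) as "patients who were ADA negative at baseline as well as at all post-baseline scheduled visit". Category 3 uses the same condition for baseline positives: "Treatment-reduced ADA, defined as patients who were ADA positive at baseline and ADA negative at all post-baseline scheduled visit". Category 6 is "Inconclusive, defined as patients who were ADA negative or positive at baseline for whom some post-baseline ADA response assessments are missing", with every other post-baseline result negative. Categories 2, 4 and 5 are different in kind, because one positive post-baseline result is enough; category 2, for example, is "patients who were ADA negative at baseline and ADA positive at at least one post-baseline scheduled visit". Two totals follow. Category 7 is "Total prevalence of pre-Ab i.e., patients in categories 3, 4, and 5 combined", and category 8 (treatment-emergent positive) adds categories 2 and 5.

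The zilucoplan sub-protocol, section 1.2, schedules ADA blood on Day 1, on the day of discharge, and on Days 15 and 29. Footnote u limits the last two: "This assessment will be performed if the patient is in the hospital". Footnote a keeps the Day 15 and Day 29 visits going by telemedicine after discharge, so they remain scheduled visits at which no blood is drawn.

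Master SAP 6.4 maps discharge data to a scheduled visit by window (Day 15 ±2 days, Day 29 ±3 days). COV-01-005 SAP 5.3 admits to the ADA set any patient in the safety set, randomized to this sub-protocol, with one evaluated sample, baseline-only patients included.

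**The concern.** Pre-existing antibody is a fact about the baseline sample. Category 7 makes it depend on later sampling: a patient known to be positive at baseline counts only if the later series is complete or contains a further positive. The baseline row of the by-visit table in the same section would show all baseline positives, so one report could carry two different figures.

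Separately, a patient who follows the protocol exactly can fail category 1. Take someone negative on Day 1, discharged on Day 10 and negative at discharge. No Day 15 or Day 29 blood is due, but on a literal reading two scheduled visits have no result and the patient is Inconclusive. Discharge follows recovery, so category 1 would be left mainly with slow recoverers, and the arms would be sorted differently if they recover at different speeds. Because the SAP does not say whether a sample that was never due counts as missing, two programmers could produce very different tables from the same data.

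**Working it through.** **1. Inputs.** The documents state no ADA rate. The only usable figures are the planning assumptions in Master SAP 7.1: median recovery 11 days (active) and 15 days (placebo), 490 recoveries in 700 patients, Day 29 mortality 8.25% and 15%. The planning set these come from reproduces. For 490 events and a hazard ratio of 1.364, √(490/4) × ln 1.364 − 1.96 = 3.436 − 1.96 = 1.476, or 93.0% power with no interim looks. Adding the two futility looks (p = 0.503 at 123 events, p = 0.175 at 270) gives the stated 88.3%, and the stated null stopping probabilities of 0.497 and 0.346.

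**2. Recovery as a proxy for discharge.** With exponential recovery, the share recovered by day t is 1 − 2^(−t/median).

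| Day | Active | Placebo |
|---|---|---|
| 15 | 0.611 | 0.500 |
| 28 | 0.829 | 0.726 |
| 29 | 0.839 | 0.738 |

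The Day 29 values give 350 × (0.839 + 0.738) ≈ 552 recoveries, against 490 planned (490/700 = 70%). The exponential curve therefore runs somewhat fast. Discharge lags of 0, 2 and 5 days after recovery (an assumption) were used to cover this.

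**3. Category rules applied to patients negative on every sample.** Simulation, 200,000 patients per scenario, deaths at the planning rates spread evenly over 29 days. Entries are the percentage classed Inconclusive at lags of 0, 2 and 5 days.

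| Results required | Active | Placebo |
|---|---|---|
| Days 15 and 29 | 84.4, 82.2, 78.5 | 76.4, 74.2, 70.5 |
| Days 15 and 29, discharge sample mapped by window | 81.0, 78.5, 73.8 | 72.9, 70.3, 66.1 |
| Days 15 and 29 and day of discharge | 99.1, 98.9, 98.7 | 99.0, 98.9, 98.7 |

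Deaths are a small part of the first row. At lag 0, discharge before Day 29 alone gives 82.9% and 72.6% (Day 28 values above), so deaths add 1.5 and 3.8 points. At lag 5, discharge alone gives 1 − 2^(−23/11) = 76.5% and 1 − 2^(−23/15) = 65.5%, so deaths add about 2 and 5 points.

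If samples not due after discharge are not counted as missing, the contribution of discharge is 0%.

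**4. Effect of window mapping.** One discharge sample can fill Day 15 or Day 29, not both. It helps a patient with a Day 15 sample who is discharged on Days 26-28. It does not help a patient discharged before Day 13, who is still without both visits.

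**5. Prevalence.** Let b be the number positive at baseline, and k the number of these with no positive post-baseline result and an incomplete (or empty) post-baseline series. Category 7 reports b − k; the correct count is b. The relative loss is k/b = s × q, where s is the share with an incomplete series and q the share of those with no later positive. The documents do not give q. At q = 0 the loss is 0; at q = 1 it equals s, which on the literal readings is the range in step 3. If samples not due are excluded, s shrinks to patients who missed a due sample or have no post-baseline sample, also not given. The error is never in the other direction.

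**The case against.** The strongest reply is that footnote u makes the Day 15 and Day 29 samples conditional, so after discharge nothing is due and nothing is missing. On that reading discharge makes nobody Inconclusive. The 99% result, an almost empty category 1, also suggests that a fully literal reading was never intended; discharge is not among the nominal visits in Master SAP Appendix 2. This stands as far as it goes: the SAP is silent, and the 66-99% is conditional on one answer to an open question. It does not rescue category 7, which is wrong under either answer.

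Other parts of the reply also stand. Recovery includes score 6, still in hospital, so it is an imperfect proxy for discharge. The sub-protocol randomized 108 patients, enrollment stopped early, and the ADA output is descriptive. Holding back the label negative from an incomplete series is a defensible conservative choice where a due sample was missed.

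A reader might infer more than the documents support:

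- *That every category needs a complete series.* Only categories 1 and 3 do.
- *That only a patient still in hospital at Day 29 can be negative.* The ±3-day mapping admits some patients discharged on Days 26-28.
- *That baseline positives generally drop out of the prevalence.* Any later positive keeps them in category 4 or 5.
- *That almost no patient would be ADA negative.* This follows only if the discharge sample is required as well; otherwise about 16-34% remain.

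**Conclusion.** The point holds in two parts. Category 7 is misdefined however missing is read: it omits known baseline positives and can only understate prevalence, by an amount the documents do not give. The all-visits rule for categories 1 and 3 conflicts with the sampling schedule. Taken literally, it moves about 66-84% of always-negative patients to Inconclusive when Days 15 and 29 are required, with or without window mapping, and about 99% when the discharge sample is required too. Those figures rest on exponential recovery at the planned medians, recovery as a proxy for discharge with a lag of 0 to 5 days, planned mortality, and samples not due being counted as missing. Without that last assumption the contribution of discharge is 0%.

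It would go too far to say that the immunogenicity reporting as a whole fails. The all-visits rule does not touch categories 2, 4, 5 and 8, the by-visit positive and negative counts, or the listing of all ADA data.

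**What to change.** Amend COV-01-005 SAP section 20 as follows.

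- **Category 7:** all baseline-positive patients, over all patients with a baseline ADA result.
- **Missing ADA assessment:** a sample that was due and not obtained. Due means in hospital at Day 15 or Day 29, or the day of discharge for a discharged patient.
- **Categories 1 and 3:** at least one post-baseline result, all of them negative, and no due sample missing.
- **Category 6:** no post-baseline result, or at least one due sample missing with all other results negative. With the line above, the categories do not overlap.
- **Category 1 output:** add the study day of the last ADA sample.

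The cost is SAP wording and derivation code, with no new samples. The small downside is that some negatives will rest on an early discharge sample, which the day of the last sample makes visible.
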